9. STUDY SCHEDULE

This section describes conduct of the study in chronological order, detailing procedures for data collection at each of the time points.

Table 1: Tabulated Study Schedule

A tabulated study schedule to illustrate all data collection at each time point of the study;

TIMEPOINT	Week -2 (Surgery)	Baseline ¹ (+2 weeks)	Week 4 ¹ (+6 weeks)	Week 5 ² (+7 weeks)	Week 10 ² (+12 weeks)	End of Study	
PRE-TRIAL:							
Surgery	X						
Patient Information	X						
ENROLMENT:							
Eligibility screen		X					
Informed consent		X					
Baseline fracture characteristics		X				X ³	
Baseline socio-demographics		X					
Randomisation		X					
INTERVENTIONS:							
Plaster Cast		●————●					
Removable Support Boot		●————●					
Time to fit / remove Intervention		X	X				
ASSESSMENTS:							
Olerud & Molander Questionnaire		X		X	X		
EQ-5D-5L Questionnaire		X	X	X	X		
Resource Use⁴			X		X		
Return to usual activities					X		
Range of Ankle Movement			X				
Weight Bearing Status			X				
Circumferential Swelling			X				
Complications			X		X		
Serious Adverse Events		●————●					
Healing Status						X ³	
Participant Interviews					X		

¹ Baseline and 4-week follow-up data collected during participants' clinic visits

² 5-week and 10-week follow-up data completed by participants at home (sections 9.5 and 9.6)

³ Healing status, fracture classification and pattern will be obtained by CI's blinded review of X-rays at end of study

⁴ Resource use data collected primarily by patient-completed questionnaire. Services delivered by the treating hospital will be obtained by research teams' review of hospital records

9.1. Pre-trial patient management

Patients will undergo surgical fixation in accordance with local policy and practice. After surgery and prior to discharge, patients will be fitted with a 'back slab' plaster; a plaster support which temporarily immobilises the broken ankle and which has an incomplete front section so as to accommodate swelling. Prophylactic anticoagulation therapy (minimising risk of developing a blood clot) will be given as appropriate. This post-operative management will be provided in accordance with local policy and practice before the patient is discharged from hospital.

9.2. Patient identification and approach

Surgeons at participating sites will be made aware of the study and the profile of potentially eligible patients by the PI. Potentially eligible patients will be approached by a member of the local research team (employees of the Hospital Trust, usually research physiotherapists or research nurses) to discuss the ART trial - preferably prior to being discharged from hospital following their ankle surgery. In the event that the patient is discharged before they can be approached, a member of the research team may contact the patient at home. The research team member will briefly describe the trial and will provide the patient with a Participant Information Sheet (PIS). Patients will be advised that they will be invited to take part in the trial when they attend their routine post-operative outpatient visit, and that they may contact a member of the research team in the meantime with any queries (contact details given in the PIS). Between receiving the PIS and attending their routine post-operative outpatient visit, patients will have up to 2 weeks to consider participating in the trial but importantly, they must have no less than 24 hours. A record of the number of patients undergoing surgical fixation for unstable ankle fracture and those approached will be maintained by the research team at each site.

9.3. Baseline clinic visit (2 weeks post-surgery)

9.3.1. Consent process

At the routine post-operative outpatient visit, typically around two weeks after surgery, patients will be approached by the PI or delegated member of the research team in order to discuss participation in the trial. Potentially eligible patients who express willingness to participate will be asked to provide consent in accordance with Good Clinical Practice. The consent process will involve a full explanation of the trial given by the person taking consent. The person responsible for taking consent will be trained in GCP and Informed Consent. Patients will be advised that they are under no obligation to take part and that their ongoing care will be unaffected if they choose not to take part. Patients who choose not to take part will be asked to provide a reason for declining, but will be told that they do not have to give a reason if they wish not to. Patients will also be advised that they are free to withdraw from the trial at any time and that doing so will not affect their ongoing care.

Following this discussion, patients who are willing to participate will be asked to complete, sign and date the trial consent form, which will also be signed and dated by the person obtaining consent.

Eligibility will be determined via clinical assessment, patient questioning and review of the patients' hospital notes. The PI is responsible for confirming eligibility and for

obtaining consent but may delegate these duties appropriately to other members of the research team. Such delegation will be captured on a site-specific site delegation log. Any person obtaining written informed consent must have current GCP training and have received trial-specific training from the trial team. No clinical trial procedures will be conducted prior to taking consent from the participant.

A copy of the signed Informed Consent form will be given to the participant. The original signed form will be retained in the Investigator Site File and a copy placed in the patient's hospital notes. Note that any new information that arises during the trial that may affect participants' willingness to take part will be reviewed by the Trial Steering Committee. If necessary, this information will be communicated to all participants and they will be asked to re-confirm consent in light of the new information.

Patients who are found to be ineligible or who are unwilling to participate will be managed as per usual care. Reasons for non-participation (where given) will be recorded by the research team at each site.

9.3.2. Baseline questionnaire completion

After eligibility has been confirmed and written consent obtained, and prior to randomisation, patients will be provided with a questionnaire booklet to be completed during the visit. The baseline questionnaire booklet will comprise the following questions;

- Demographic and socio-economic questions
- Pre-injury Olerud and Molander (1984) ankle score (see section 7.1)
- EQ-5D-5L (see section 7.2)

9.3.3. Baseline CRF completion

A member of the research team will transcribe the following information from the patient's hospital record into the trial case report form (CRF):

- Participant information; name, date of birth, address contact details and preferred method of contact (to facilitate sending and retrieval of questionnaires and reminder alerts.)
- Fracture information; date of fracture, date of surgery, fracture side, complexity (Simple or comminuted fracture.)
- Weight and Height to compute Body Mass Index (BMI); participants may be weighed and measured at this visit if a recent weight and height is not available in the hospital notes.

9.3.4. Randomisation

Following completion of baseline information collection, a member of the research team will randomise the participant to one of the two treatment groups; Removable support boot, or plaster.

Patients will be randomised in order to minimise systematic bias, using a secure web-based system designed and maintained by the Peninsula Clinical Trials Unit

(PenCTU) according to the Unit's standard operating procedures. Computer generated randomisation codes prepared by the PenCTU will be kept secure, with access restricted to the data management team at the PenCTU. Participants will be allocated to the support boot group (intervention) or to the plaster group (control) in a 1:1 ratio, using random, even, block sizes between 2 and 8 to generate the allocation sequence and achieve balance in the numbers of participants allocated to each group. Randomisation will be stratified by site. The web-based randomisation system will be accessed securely via unique log-in details provided to each local team member by the CTU. The system ensures that allocation is appropriately concealed until the point of randomisation.

Upon randomisation, each participant will be assigned a unique Trial Number which will be used as the principal identifier on trial data collection forms and questionnaires. The research team member will disclose the allocation to the participant and will ensure the allocation is followed as described below.

9.3.5. Provision of treatment

Following allocation to treatment group, the patient will be directed to the facility (e.g. plaster room) in order to receive treatment. The support boot/below knee plaster (as per allocation) will be fitted by the plaster room technicians in accordance with local practice once any clips/stitches are removed. The time taken and materials used by plaster room technicians in fitting the boot/plaster in each case will be recorded on a designated form by the research team. A physiotherapist trained in the requirements of the study protocol will provide the patient with an advice leaflet specific to the participant's treatment allocation and teach them the exercises detailed. A member of the research team will also record the time the physiotherapist spends on educating patients about their treatment and the associated leaflets. These data will be used to cost the delivery of treatment in both arms for the economic evaluation as described in section 12.4.

9.3.6. Provision of Patient Diary

Completion of follow-up questionnaires may be difficult for some patients. Missing data and recall bias are frequent problems when asking patients to retrospectively recollect events at follow-up time points.

At baseline and 4 weeks, a research team member will also therefore provide each participant with a trial-specific Patient Diary and verbal instructions as to how this could be used. Participants will be advised to use the diary as an aide-memoire to prospectively record adverse events, healthcare resource use (visits to or from healthcare professionals such as GPs, community nurses, hospital admissions etc.) to facilitate completion of questionnaires at the next visit.

9.3.7. End of baseline visit procedures

The research team will ensure the following before the patient leaves the hospital:

- The baseline questionnaires are as complete as possible. If data are missing, any missed questions will be highlighted to the patient.
- The patient has the correct advice leaflet (according to their treatment allocation) and the Patient Diary.
- The patient is aware of when their next appointment is scheduled.

A member of the research team will subsequently ensure that:

- The patient's participation in the trial is appropriately recorded in the hospital records and that hospital notes are labelled / annotated in accordance with local practice.
- The CRF with data collected on delivery of treatment is completed.
- The approved GP letter is sent to the patient's General Practice.

The original completed questionnaires and CRF pages will be sent to PenCTU using FREEPOST envelopes – copies of these should be retained at the local site.

9.4. 4-week follow-up visit (6 weeks post-surgery)

Participants in both treatment groups will attend a routine six-week post-operative appointment. Participants will have their plaster or support boot removed (unless otherwise indicated), routine clinical assessments and x-rays will be performed to guide the participant's subsequent management. 4-week follow up data will be collected at this visit.

9.4.1. 4-week follow-up questionnaire completion

The participant will be provided with a questionnaire to be completed during the visit. The 4-week questionnaire booklet will comprise:

- EQ-5D-5L (see section 7.2)
- Resource use questionnaire (see section 7.4)

Participants will be encouraged to use their Patient Diary to facilitate answering questions as appropriate.

9.4.2. 4-week follow-up CRF completion

Following removal of the plaster or support boot, the patient will receive routine clinical assessment and a member of the research team will transcribe the following information from the patient's hospital records into the trial case report form (CRF):

- Range of ankle movement (see section 7.2)*
- Weight-bearing status (see section 7.2)
- Circumferential swelling (see section 7.2)*
- Complications and associated antibiotic usage (see section 7.2)
- Time required to remove boot/ or plaster and re-fit if necessary (see section 7.4)
- Mobilisation and adherence to exercise (see section 7.7)

*Range of movement assessments and circumferential swelling measurements must be conducted by a physiotherapist trained in the requirements of the study protocol and documented in the patient's record.

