The profiles from the patients’ answers to the EQ-5D-5L will be weighted using the EuroQol’s published United Kingdom societal utility tariffs to produce a composite, utility based quality of life score and EuroQol has piloted the 5L valuation scores²⁵. If final scores are not available by the end of the trial, the crosswalk developed by EuroQol from the three level scores will be used. Quality Adjusted Life Years will then be created from the four time point utility scores assuming a linear change between the time points and using the area under the curve approach. Incremental QALY gains between arms will then be estimated using regression analysis adjusted for baseline utility and site, age and fracture complexity variables.

Multiple regression will be used to investigate differences between the two groups in the other continuous outcomes measured at four weeks post-baseline (e.g. degrees of range of movement (dorsiflexion, plantarflexion, inversion, eversion), circumferential swelling and 10 weeks (e.g. return to daily activities on 0-10 scale). Complications in the two groups (presence and severity), healing status (displaced / undisplaced and evidence of post-operative fracture healing (yes/no)), employment status at 10 weeks, driving status and weight bearing status will be investigated using logistic regression (binomial or multinomial depending on the number of categories), again taking study site, age and fracture complexity into account. Survival analysis will be used to investigate the time from randomisation to starting to drive again. Supplementary analysis (b) to (e) as described for the primary outcome will also be conducted for secondary outcomes.)

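### The only stated completeness check on the baseline booklet comes after the arm is disclosed, so missed EQ-5D-5L or pre-injury ankle score items can be answered by a patient who knows the allocation

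*Protocol*

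**What the plan says.** The opening of section 9 sets the order of events: "This section describes conduct of the study in chronological order". Within the baseline visit the steps are:

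- **Section 9.3.2.** After consent "and prior to randomisation, patients will be provided with a questionnaire booklet to be completed during the visit". The booklet holds demographic and socio-economic questions, the pre-injury ankle score and EQ-5D-5L.
- **Section 9.3.4.** "Following completion of baseline information collection, a member of the research team will randomise the participant". The participant is then told the allocation.
- **Section 9.3.5.** The boot or plaster is fitted, and a physiotherapist gives out the arm-specific leaflet and teaches its exercises.
- **Section 9.3.7.** Before the patient leaves the hospital, the team ensures the following: "The baseline questionnaires are as complete as possible. If data are missing, any missed questions will be highlighted to the patient". The next item in the same list confirms that the leaflet matches the allocation.

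Section 12.2.3 builds QALYs from the utilities at four time points, baseline included, and compares arms by a regression "adjusted for baseline utility and site, age and fracture complexity variables". Section 12.4 repeats the baseline-utility adjustment for the economic result. Section 12.2.2 leaves the pre-injury ankle score out of the primary analysis. It uses the score as the covariate in sensitivity analysis (b) and as the reference for change to 10 weeks, including the proportion worse by at least 10 points, and compares those figures between arms.

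**The concern.** A baseline value is a safe covariate because allocation cannot have influenced it. That protection is lost for any item answered after the patient has been told the arm.

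The trial is open to the patient (section 5.2), and the protocol itself expects EQ-5D-5L to respond to the device: section 7.2.3 attributes the 4-week measurement to the restriction caused by boot or plaster. An EQ-5D-5L item filled in after fitting may thus carry some treatment effect or some reaction to the allocation. The pre-injury ankle score is less exposed, because it asks about a past state that the device cannot alter. Only recall or attitude could shift it, and its activity item is fixed at 20 for everyone at baseline (section 12.2.1).

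At stake are the QALY comparison, sensitivity analysis (b) and the comparison of pre-injury with 10-week function. As written, nobody could later tell which items were answered late, because such entries are not marked.

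**Working it through.** **Order of steps.** The protocol states no figure on this point, so the main check is to set sections 9.3.4 and 9.3.7 side by side.

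1. If section 9.3.4 means that every item has been checked before randomisation, the section 9.3.7 check has nothing left to fill.
2. If section 9.3.7 does find a gap, baseline collection was complete only in the sense that the booklet had been worked through. The gap is then pointed out to a patient who knows the arm.
3. Section 9.3.4 names no item-level check, and no other section describes one before randomisation. Nothing forbids entries after allocation or asks for them to be flagged.

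The text therefore permits the second case. It does not show how often it would occur.

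**Weight of baseline utility in the QALY.** Utilities are taken at weeks 0, 4, 5 and 10 (section 7.2.3) and joined by straight lines (section 12.2.3). The trapezoid weights in years are:

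- week 0: (4/2)/52 = 0.0385
- week 4: ((4+1)/2)/52 = 0.0481
- week 5: ((1+5)/2)/52 = 0.0577
- week 10: (5/2)/52 = 0.0481

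The total is 10/52 = 0.1923, so baseline carries 0.0385/0.1923 = 20%.

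**Illustrative size.** Let p be the proportion of patients who answer an EQ-5D-5L item late, d the between-arm difference that late answering adds to their utility, and b the slope of QALY on baseline utility. The spurious difference in mean baseline utility is p × d. It adds 0.0385 × p × d to the QALY difference, and the covariate adjustment removes b × p × d, so

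net shift = (0.0385 − b) × p × d.

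None of p, d or b is in the protocol. Assume p = 2-20% and d = 0.05-0.10, so that p × d runs from 0.02 × 0.05 = 0.001 to 0.20 × 0.10 = 0.020. Two slopes serve as reference points: b = 0.0385 if later utilities are unrelated to baseline, and b = 0.1923 if they follow it one for one. Values are at £20,000 per QALY.

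| Slope b | Size of (0.0385 − b) | QALY shift (absolute) | Value |
|---|---|---|---|
| 0.0385 | 0 | 0 | £0 |
| 0.06 | 0.0215 | 0.00002-0.0004 | under £1 to £9 |
| 0.10 | 0.0615 | 0.00006-0.0012 | £1-£25 |
| 0.1923 | 0.1538 | 0.00015-0.0031 | £3-£62 |

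For b above 0.0385 the shift is against the arm whose late answers are raised.

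**Against sampling error.** Assuming a 10-week QALY standard deviation of 0.02-0.03 and 102 patients per arm (section 12.1), the standard error of the difference is 0.02 × √(2/102) = 0.0028 to 0.03 × √(2/102) = 0.0042. At b = 0.10 the largest shift, 0.0012, is under half a standard error. Only the extreme corner (20% late, d = 0.10, one-for-one tracking) reaches 0.0031, or roughly 0.7 to 1.1 standard errors.

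**The case against.** The strongest reply is that the right order is already fixed. The booklet comes before randomisation, and randomisation follows completion of baseline collection. The list in section 9.3.7 is governed by a deadline, the patient's departure, which does not forbid an earlier check. Its other items re-confirm things already done (the leaflet from section 9.3.5, the diary from section 9.3.6), so the questionnaire item may be only a backstop. Most of this stands. It limits the exposure to stray missed items and makes the problem one of loose wording. It does not supply an earlier check, and a backstop that prompts the patient to answer after disclosure still admits post-allocation values.

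A reader might infer more than the text supports:

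- **That missed items are always answered after allocation, or that sections 9.3.4 and 9.3.7 flatly contradict each other.** The text makes late answering possible. It neither requires it nor says when in the visit the check is done, and the sections can be read together.
- **That the main effectiveness result is affected.** It is not. The primary model contains treatment arm, site, age and fracture complexity, and neither baseline score.
- **That the economic conclusion is at risk,** for instance by setting £25 beside the £31.55 gap between boot price and plaster materials in section 3 (£52.39 − £20.84). Every driving input to the £25 is assumed, so the comparison shows nothing about the decision.

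Barring all late baseline entries would also go too far. Marital status or education cannot be changed by allocation, and the imputation model in section 12.4 relies on such items.

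**Conclusion.** The point holds as a small procedural weakness. Following the protocol as written, a patient who knows the arm can supply missing EQ-5D-5L or pre-injury ankle score items, and those entries cannot later be identified. The exposed results are the QALY area under the curve and its baseline-utility adjustment, sensitivity analysis (b), and the comparison of pre-injury with 10-week scores.

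The effect is probably small, since only missed items are involved. The protocol gives no rate of late completion, no size of shift and no slope, so the range in the table shows how the answer depends on assumptions and is not an estimate of bias. No stated number in the protocol changes. The change is worth making because it prevents the problem almost for free, whereas the analysis could not detect it afterwards.

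**What to change.** 1. Move the completeness check to the end of section 9.3.2, so that missed questions are pointed out while the patient is still unaware of the arm.
2. In section 9.3.4, make that check a condition of randomising.
3. State that EQ-5D-5L and pre-injury ankle score items may not be entered or changed after randomisation, and that any still blank are treated as missing.
4. Limit the section 9.3.7 item to fixed demographic and socio-economic questions, which may still be completed before the patient leaves.

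This moves one check within the same visit and needs a line in site training. The downside is that a few baseline EQ-5D-5L or ankle score items may stay missing. A patient without a baseline utility would drop out of the complete-case QALY analysis, though section 12.4 already provides for imputing utilities. Checking before randomisation should keep such cases few.

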9.4.1. Provision of Patient Diary

Each participant will be provided with a second trial-specific Patient Diary to facilitate completion of questionnaires at the 10-week time point.

9.4.2. End of 4-week follow up visit procedures

A member of the research team will ensure the following before the patient leaves the hospital:

- A copy of the 5-week follow-up questionnaires (and a freepost envelope) will be given to participants. They will be instructed on how to complete the questionnaire using their preferred option (online, phone or post). The importance of completing the questionnaire within 3-10 days will be emphasised. Participants will be encouraged to complete the questionnaire online. If they would prefer not to use the online method, they will be encouraged to complete over the phone. Those participants, who state that they are unable to complete the questionnaire online or by telephone, will use postal completion. Participants who are completing questionnaires online will be emailed to access this approximately 3 days after their 4 week clinic appointment. Participants who have opted for telephone completion will be telephoned approximately 5 days after their 4 week clinic appointment. Participants will be encouraged to have the paper version of the questionnaire by their side during the phone call.
- The patient has their Patient Diary and is aware that they will be receiving questionnaires in approximately 6 weeks' time by post/email and that they may be contacted in the event that the questionnaires are not returned so as to prompt for return or to complete the questionnaire over the telephone.

The research team will also ensure that the patient's continuing participation in the trial is appropriately recorded in the hospital records in accordance with local practice.

Completed questionnaires and CRF pages will be sent to PenCTU using FREEPOST envelopes.

9.5. 5-week follow-up questionnaire completion

The 5-week follow-up requires participants to complete a questionnaire comprising the following:

- Olerud and Molander (1984) ankle score (see section 7.1)
- EQ-5D-5L (see section 7.2)

The aim is to collect data on primary outcome and EQ-5D-5L at 5 days after the participants 4 week clinic visit. Most participants will have had their plaster / boot removed at the 4 week appointment. It is thought that any benefits resulting from use of the boot would be apparent at this time point. The time window for a valid response will be defined as 3-10 days after the 4 week appointment. The method of data collection has been designed to minimise the risk of missing data. Too much missing data may have a negative impact on the statistical analysis and

interpretation of results (e.g. less precision and possibility of bias). For ease of communication this follow-up will be referred to as the 5 week follow-up.

PenCTU staff will monitor receipt of questionnaires and will issue reminders to patients if the questionnaire has not been returned. If a questionnaire has not been received within 8 days from the week 4 visit, attempts will be made to contact the participant by telephone and the option of completing the questionnaire by telephone will be available.

9.6. 10-week follow-up (12 weeks post-surgery)

9.6.1. 10-week follow-up questionnaire completion

The 10-week follow-up requires participants to complete a questionnaire comprising the following:

- Olerud and Molander (1984) ankle score (see section 7.1)
- EQ-5D-5L (see section 7.2)
- Resource use questionnaire (see section 7.4)
- Return to activities (see section 7.2)

PenCTU staff will issue questionnaires to participants according to a participant schedule created in the trial database through registration of randomisation and 4-week follow-up dates. The information accompanying the questionnaire will remind participants to make use of their Patient Diaries when completing the questionnaires and request that they are returned within 7 days. The time window for a valid response will be defined as 28 days from the issue of the first week 10 questionnaire. If patients have a preference to receive the questionnaire by post, a self-addressed FREEPOST envelope will be included to facilitate postal return. Participants who have opted to complete questionnaires online will be emailed to access the questionnaire. PenCTU staff will monitor the sending and receipt of questionnaires and will issue another questionnaire with a reminder if the first one has not been returned within 10 days from issue. If a completed questionnaire has not been received by 14 days from issue of the first questionnaire, attempts will be made to contact the participant by telephone. Questionnaires may be completed over the telephone if online/postal questionnaires have not been returned or are lost - if participants feel unable to complete the full questionnaire, participants will have the option of completing a subset of the questionnaire booklet by telephone. Priority will be given to collecting the Olerud & Molander ankle score and EQ-5D-5L.

9.6.2. 10-week follow-up CRF completion

Secondary care healthcare resource use information within the 10 week trial period will be collected and transcribed from the hospital records into the CRF by the local research team. Data extracted will include hospital admissions, outpatient visits, including physiotherapy sessions, day case procedures, visits to Accidents & Emergency departments and diagnostic tests or investigations conducted outside the outpatient visit tariff (See Section 7.4 Resource Use).

A small proportion of patients with complicated recoveries may need further clinical evaluation at 12-weeks post-surgery, as per standard care. The research team will

record the date when the patient was discharged or whether they returned to clinic for further follow up at 10 weeks post baseline (12 weeks-post surgery).

Completed CRF pages will be sent to PenCTU using FREEPOST envelopes.

